4.1. Overall Design

This is a Phase 3, parallel-design, open-label, randomized control study to evaluate the efficacy and safety of LY3209590 administered once-weekly compared to insulin degludec administered daily.

The study includes a 3-week screening and lead-in period, a 52-week treatment period, and a safety follow-up period approximately 5 weeks after the last visit in the treatment period.

Screening and Lead-In

Visit 1: Screening

Interested participants will sign the appropriate informed consent document(s) prior to initiating any procedures.

The investigator will review medical history, symptoms, risk factors, and other inclusion and exclusion criteria prior to any diagnostic procedures. If the participant is eligible after this review, then the site will perform the diagnostic procedures to confirm eligibility.

Visit 2: Lead-In

Participants will receive their e-diary, glucometer, and the CGM system.

Participants will receive training on

- diabetes self-monitoring and management
- study glucometer
- CGM
- electronic study diaries, and
- study requirements.

The CGM sensor will be inserted at Visit 2, and participants will be required to wear the sensor and insert a new sensor when indicated per the SoA.

Starting with Visit 2, participants must measure their FBG levels each day when possible or at a minimum 3 times per week.

Participants will continue their current diabetes therapy until randomization.

Treatment period

Visit 3 (Week 0): Randomization

This is the general flow for Visit 3

- study personnel confirm enrollment criteria
- participants are randomly assigned to an intervention group
- study personnel complete baseline procedures and sample collection
- study personnel will provide dosing training and administer the first dose of LY3209590 or insulin degludec,
- study personnel will download the CGM

- participant will continue CGM wear per the SoA, and
- study personnel complete all visit procedures.

Participants assigned to insulin degludec will continue daily administration after Visit 3.

Visit 4 (Week 1)

Study personnel and participants complete all visit procedures described in the SoA.

Study personnel will provide dosing training and observe participants administer their second dose of LY3209590, or insulin degludec.

Visit 5 through Visit 31 (Week 2 through Week 52)

Study personnel and participants complete all visit procedures described in the SoA.

The participant's median FBG will be used to titrate basal insulin dose adjustments throughout the study based on the study titration algorithm described in Section [6.5.1](#).

Participants will collect blinded CGM for

- 4 weeks prior to Visit 7, and the site will download the CGM data at Visit 7
- 4 weeks prior to Visit 15, and the site will download the CGM data at Visit 15
- 4 weeks prior to Visit 24, and the site will download the CGM data at Visit 24; and
- 4 weeks prior to Visit 31, and the site will download the CGM data at Visit 31.

The investigator or study staff will review participant e-diary compliance for

- SMBG
- hypoglycemia events, including related signs and symptoms, and
- dosing information, including date and time of doses.

Last study treatment visit: either Visit 31 (Week 52) or ED visit

Participants should complete all visit procedures in a fasting state.

Participants will return unused study intervention to the investigative site.

Assessments for the transition to non-study diabetic treatment after the participant's last dose

The investigator will determine a participant's transition from study treatment to another non-study diabetic treatment.

Participants will continue their concomitant antihyperglycemic medications at the discretion of the investigator.

Safety follow-up visits 801 and 802

Study personnel and participants complete all visit procedures described in the SoA.

Participants will collect blinded CGM for 4 weeks following Visit 31, and the site will download the CGM data at Visit 802.

The investigator will follow-up on the participant's transition from study treatment to another non-study diabetic treatment.

Participants will return study devices at the final study visit.

4.2. Scientific Rationale for Study Design

Primary endpoint

The primary efficacy measurement is HbA1c, a widely used measure of glycemic control that reflects a cumulative history of glucose levels in the preceding 2 to 3 months.

Overall design

Blinding

This is an open-label study. Investigators, participants, and study-site personnel will be unblinded to the assigned treatment. To eliminate potential biases, designated members of the Lilly study team will remain blinded throughout the study (see Section 6.3). Only a minimum number of Lilly personnel will see the randomization table and treatment assignments before the study is complete.

Study Duration

The treatment duration of 52 weeks is a reasonable time frame to observe the effects of LY3209590 compared to insulin degludec.

The follow-up visit after the last dose is designed to capture any additional safety signals and to monitor the transition from study treatment to non-study diabetic treatment.

Comparator

Insulin degludec was chosen as the comparator because it is widely accepted as the best-in-class basal insulin.

Collection of race and ethnicity data

In this study, collection of demographic information includes ethnicity (where permissible) and race. The scientific rationale is based on the need to assess variable response in safety or efficacy based on race or ethnicity. This question can be answered only if all the relevant data are collected.

4.3. Justification for Dose

The dosing guidance for starting doses and dose titrations of LY3209590 and insulin degludec are derived based on findings from Phase 2 studies and model-based simulations. These data informed the development of a titration algorithm to safely and efficiently initiate and guide LY3209590 and insulin degludec dose adjustments to achieve the same glycemic goals of FBG between 80 and 120 mg/dL (4.4 and 6.6 mmol/L), while minimizing hypoglycemia risk.

See Section 6.5 for dose modification and titration details.

LY3209590

Initial loading dose

The initial loading dose aims to optimize and accelerate glycemic control by allowing participants to reach a steady-state concentration faster. The use of a single one-time-only loading dose enables participants to achieve concentrations close to steady state within a few

days rather than a period of weeks. This approach minimizes the significant titrations while reaching steady state.

Participants randomly assigned to LY3209590 will receive a single loading dose of 300 U of LY3209590, which equals 3 times the starting weekly dose of 100 U.

This approach is supported by the Phase 2 Study BDCL and PK model-based simulations.

Starting weekly dose

The second dose is the starting weekly dose of 100 U, unless hypoglycemia is observed after the initial loading dose, requiring a dose reduction.

Dose Adjustments

Assessments for dose adjustment will occur from the third dose onwards. Dosing will be individualized based on FBG and hypoglycemia events, and adjustments should occur weekly from Visits 5 to 15 (Weeks 2 to 12) and then every 4 weeks thereafter.

Insulin degludec

Insulin degludec will be titrated to achieve the FBG target using an algorithm that is patterned after the well-established Riddle algorithm but modified to balance efficacy and hypoglycemia risk for the same FBG targets as LY3209590.

Starting dose

The starting dose is 10 U, consistent with the insulin degludec label.

Dose Adjustments

Dosing will be individualized based on FBG and hypoglycemia events, and adjustments should occur weekly from Visits 4 to 15 (Weeks 1 to 12) and then every 4 weeks thereafter.

4.4. End of Study Definition

The end of the study is defined as the date of the last scheduled procedure shown in the SoA for the last participant in the study.

A participant is considered to have completed the study if the participant has completed all periods of the study including the last scheduled procedure shown in the SoA.

5. Study Population

Prospective approval of protocol deviations to recruitment and enrollment criteria, also known as protocol waivers or exemptions, is not permitted.

5.1. Inclusion Criteria

Participants are eligible to be included in the study only if all of the following criteria apply:

Age

1. Are ≥ 18 years of age inclusive, at screening, or older per local regulations.

Type of Participant and Disease Characteristics

2. Have a diagnosis of T2D according to the World Health Organization criteria.
3. Have an HbA1c of 7.0%-10.5%, inclusive, as determined by central laboratory at screening.
4. Are on a stable treatment with 1 to 3 antihyperglycemic medication, for at least 3 months prior to screening, and willing to continue the stable treatment for the duration of the study. Therapies must be used in accordance with the corresponding local product label.

These antihyperglycemic medications are accepted in the study

- DPP-4 inhibitors
- SGLT2 inhibitors
- biguanides, such as metformin
- alpha-glucosidase inhibitors
- GLP-1 receptor agonists, oral or injectable
- sulfonylureas, or
- thiazolidinediones.

5. Are insulin naïve.

Exceptions:

- short-term insulin treatment for a maximum of 14 days, prior to screening, and
- prior insulin treatment for gestational diabetes.

Weight

6. Have a body mass index ≤ 45 kg/m².

Contraceptive or barrier requirements

Contraceptive use by participants should be consistent with local regulations regarding the methods of contraception for those participating in clinical studies.

7. Male participants: no male contraception required except in compliance with specific local government requirements.

Female participants: for the contraception requirements of this protocol, see Section 10.4.

Study Procedures

8. Are reliable and willing to make themselves available for the duration of the study and are willing and able to follow study procedures as required, such as
 - self-inject intervention
 - store and take provided study interventions as directed
 - maintain an electronic study diary
 - use only the glucometer supplied for use in the study, and
 - wear the CGM device as directed, see Section 8.1.1.2.

Note: The use of personal, non-study CGM device will not be allowed.

Note: persons with physical limitations who are not able to perform the injections must have the assistance of an individual trained to inject the intervention.

Informed Consent

9. Are capable of giving signed informed consent as described in Section 10.1.3, which includes compliance with the requirements and restrictions listed in the ICF and in this protocol.

Other Inclusions

10. Have usual wake and sleep patterns, such that midnight to 0600 hours will reliably reflect a usual sleeping pattern.

5.2. Exclusion Criteria

Participants are excluded from the study if any of the following criteria applies:

Medical conditions

11. Have a diagnosis of T1D, latent autoimmune diabetes, or specific type of diabetes other than T2D, for example, monogenic diabetes, diseases of the exocrine pancreas, or drug-induced or chemical-induced diabetes.
12. Have a history of >1 episode of ketoacidosis or hyperosmolar state or coma requiring hospitalization within 6 months prior to screening.
13. Have had severe hypoglycemia episodes within 6 months prior to screening.
14. Have a history of renal transplantation, are currently receiving renal dialysis, or have an estimated glomerular filtration rate <20 mL/min/1.73 m² as calculated by the Chronic Kidney Disease-Epidemiology equation, determined by central laboratory at screening.
15. Have had a blood transfusion or severe blood loss within 90 days prior to screening.
16. Have known hemoglobinopathy, hemolytic anemia or sickle cell anemia, or any other traits of hemoglobin abnormalities known to interfere with the measurement of HbA1c.
17. Have had New York Heart Association Class IV heart failure or any of these cardiovascular conditions within 3 months prior to screening
 - acute myocardial infarction
 - cerebrovascular accident (stroke), or
 - coronary bypass surgery.

18. Have had gastric bypass (bariatric) surgery, restrictive bariatric surgery, for example Lap-Band, or sleeve gastrectomy within 1 year prior to screening.
19. Have had a significant weight gain or loss within 3 months prior to screening, for example, $\geq 5\%$.
20. Have acute or chronic hepatitis, cirrhosis, or obvious clinical signs or symptoms of any other liver disease, except non-alcoholic fatty liver disease (that is, study participants with non-alcoholic fatty liver disease are eligible for participation), and/or have elevated liver enzyme measurements, as determined by the central laboratory at screening and as indicated below:
 - a. Total bilirubin $>2x$ ULN, with the exception of previously diagnosed Gilbert's disease
 - b. ALT or serum glutamic pyruvic transaminase $>3x$ ULN
 - c. AST or serum glutamic oxaloacetic transaminase $>3x$ ULN, or
 - d. ALP $>2.5x$ ULN.
21. Have a history of an active or untreated malignancy or are in remission from a clinically significant malignancy within 5 years prior to screening.

Exceptions:

- Basal cell or squamous cell skin cancer.

22. Are at increased risk for developing cancer or a recurrence of cancer.
23. Have a history of or current significant psychiatric disorders considered clinically significant, in the opinion of the investigator.
24. Have a history or presence of an underlying disease, or surgical, physical, or medical condition that, in the opinion of the investigator, would potentially affect participant safety within the study or interfere with the interpretation of data.
25. Have a known hypersensitivity or allergy to any of the study interventions or their excipients.

Prior or Concomitant Therapy

26. Have received these diabetes treatments within 30 days prior to screening
 - glinides
 - glimins
 - pramlintide, or
 - insulin or any insulin containing product.
27. Are receiving or received systemic glucocorticoid therapy for >14 days within the month before screening.

Exceptions:

- replacement therapy for adrenal insufficiency
- topical, intraocular, intranasal, or inhaled preparations, or
- intra-articular injection.

Prior or Concurrent Clinical Study Experience

28. Are currently enrolled or have participated within the last 30 days in a clinical study involving an investigational intervention or any other type of medical research judged not to be scientifically or medically compatible with this study. If the previous investigational intervention has a long half-life, 3 months or 5 half-lives, whichever is longer, should have passed prior to Visit 1.
29. Have previously completed or withdrawn from this study after having signed the ICF or any other study investigating LY3209590 after receiving at least 1 dose of the study basal insulin.

Other Exclusions

30. Have hypoglycemia unawareness in the opinion of the investigator.
31. Are women who test positive for pregnancy or intend to become pregnant.
32. Are women who are lactating or breastfeeding.
33. Have evidence of any substance use disorder of any severity defined by the Diagnostic and Statistical Manual of Mental Disorders-5, within 6 months prior to screening.

Exceptions: nicotine or caffeine.

34. Are Lilly employees or are employees of any third party involved in the study who require exclusion of their employees.
35. Are investigator site personnel directly affiliated with this study and/or their immediate families. Immediate family is defined as a spouse, parent, child, or sibling, whether biological or legally adopted.
36. Are unsuitable for inclusion in the study in the opinion of the investigator.

5.3. Lifestyle Considerations**Diabetes management counseling**

Qualified study personnel will provide diabetes management counseling, which will include instructions on diet and exercise and education about the signs, symptoms, and treatment of hypoglycemia, should it occur. Diabetes self-management counseling may be reviewed throughout the study, as needed.

Dietary and exercise considerations

Study participants should generally follow a healthy meal plan and continue their usual exercise habits throughout the course of the study.

Dietary and exercise restrictions

Study participants should not initiate an intensive diet or exercise program with the intent of reducing body weight at any time during the study, other than the lifestyle and dietary measures for diabetes treatment.

Blood donation

Study participants should not donate blood or blood products during the study or for 4 weeks following their last study visit.

5.4. Screen Failures

A screen failure occurs when a participant who consents to participate in the clinical study is not subsequently randomly assigned to study intervention. A minimal set of screen failure information is required to ensure transparent reporting of screen failure participants to meet the Consolidated Standards of Reporting Trials (CONSORT) publishing requirements and to respond to queries from regulatory authorities. Minimal information includes demography, screen failure details, eligibility criteria, and any SAE.

Individuals who do not meet the criteria for participation in this study (screen failure) will not be rescreened.

5.5. Criteria for Temporarily Delaying Enrollment of a Participant

This section is not applicable to this study. All entry criteria must be met within the specified intervals in the SoA.

6. Study Intervention(s) and Concomitant Therapy

Study intervention is defined as any investigational intervention(s), marketed product(s), placebo, or medical device(s) intended to be administered to or used by a study participant according to the study protocol.

Investigators and other study personnel are expected to treat participants according to the nationally established standards of care for diabetes management in respective participating countries, except where that treatment would be in conflict with the protocol-provided treatment requirements. If there are no local or national standards of care for diabetes, the investigators should follow current published standards of care from the American Diabetes Association.

6.1. Study Intervention(s) Administered

LY3209590 and insulin degludec will be dispensed at the study visits summarized in SoA.

Returned LY3209590 or insulin degludec should not be re-dispensed to the participants.

This table lists the interventions used in this clinical study.

Intervention Name	LY3209590	Insulin degludec
IMP and NIMP/AxMP	IMP	IMP
Authorized as defined by EU Clinical Trial Regulation^a	No	Yes
Use	Experimental	Active comparator
Type	Biologic	Biologic
Dose Formulation	Solution	Solution
Unit Dose Strength(s)	500 units/mL	100 units/mL
Dosage Level(s)	Individualized dosing (see Section 6.5.1)	Individualized dosing (see Section 6.5.2)
Frequency of Administration	Once weekly	Once daily
Route of Administration	Subcutaneous	Subcutaneous

Abbreviations: AxMP = auxiliary medicinal product; IMP = Investigational Medicinal Product; NIMP = non-investigational medicinal product.

^a Study interventions identified as authorized are used in accordance with the terms of their marketing authorizations.

LY3209590 frequency of administration and guidance for missed doses

LY3209590 should be administered once weekly at approximately the same time and day each week. If a dose is missed, it should be administered as soon as possible if at least 3 days (72 hours) remain until the next scheduled dose. If less than 3 days remain before the next scheduled dose, skip the missed dose and administer the next dose on the regularly scheduled day.

In each case, participants can then resume their regular once-weekly dosing schedule.

The day of weekly administration can be changed, if necessary, only if the last dose has been administered at least 3 days earlier.

Insulin degludec frequency of administration

Insulin degludec should be administered daily at approximately the same time each day.

Anatomical Location of Injections

For both LY3209590 and insulin degludec, participants should rotate injection sites from one injection to the next, even when injecting within the same region. Injections may be administered in the abdomen, thigh, arm, or buttock. Refer to the IFU for complete instructions on dose administration.

Packaging and labeling

Study interventions will be supplied by the sponsor or its designee in accordance with current Good Manufacturing Practice. Study interventions will be labeled as appropriate for country requirements.

6.1.1. Medical Devices

LY3209590 or insulin degludec will be provided as a solution in a prefilled pen injector for the administration of either LY3209590 or insulin degludec.

Instructions for device use are provided in the “Instructions for Use.”

All Product Complaints, including malfunction, use error and inadequate labeling, shall be documented and reported by the investigator throughout the clinical investigation (see Section 8.3.1) and appropriately managed by the sponsor.

6.1.2. Rescue Medicine for Management of Severe or Persistent Hyperglycemia

If a participant develops severe, persistent hyperglycemia after randomization, optimization of concomitant antihyperglycemic medication and/or the addition of an allowed agent for rescue therapy should be considered after investigator assessment, based on conditions described in this table.

Average of FBG over 2-week period	Timing of events
>270 mg/dL (15 mmol/L)	From Visit 15 until 17 (Week 12 to 16)
>240 mg/dL (13 mmol/L)	After Visit 17 until 19 (Week 16 to 20)
>200 mg/dL (11 mmol/L)	After Visit 19 until 31 (Week 20 to end of study treatment at Week 52)

First, investigators should confirm participant compliance with the assigned intervention and that they do not have an acute condition causing severe hyperglycemia.

Rescue therapy will begin with dose optimization of the participant’s current concomitant antihyperglycemic medications. Then consider the addition of an allowed agent for rescue therapy (see Section 6.8.3), if applicable, so the participant is taking up to 3 antihyperglycemic medications at effective doses before considering prandial insulin rescue therapy.

If severe, persistent hyperglycemia is not improving in spite of compliance with the assigned therapeutic regimen and optimization of other concomitant glucose-lowering agents, the addition of prandial insulin may be considered.

Participants who receive rescue therapy for hyperglycemia management should also continue administering either LY3209590 or insulin degludec for the remaining period in the study.

Participants who require a non-study basal insulin or insulin mixture as rescue therapy must discontinue study basal insulin therapy (LY3209590 or insulin degludec). The participant will remain in the study and follow procedures for the remaining study visits.

The investigator should ensure that the participant met the criteria for severe or persistent hyperglycemia before initiating rescue medicine and document this in the source files.

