2.3.1. Risk Assessment

Potential risks for this study

The potential risks associated with LY3209590 include

- hypoglycemia
- hyperglycemia
- hypersensitivity reaction
- injection site reactions, for example, injection site rash, erythema, or pruritus or lipohypertrophy
- immunogenicity, and
- cardiovascular risks.

It is expected that the known risks would be similar to other insulins.

Safety data available to date suggest that there is no increased risk to participants' safety with LY3209590 treatment compared to insulin degludec.

Potential risks for the LY3209590-prefilled pen device are described in the "Instructions for Use".

Management of Risks

Sections [5.1](#), [5.2](#), [6.1.2](#), [6.8.1](#), and [8.3](#) address known potential risks associated with LY3209590.

Protocol risk management measures***Participant education for hypoglycemia***

After signing informed consent, all participants will be educated about signs and symptoms of hypoglycemia, how to treat hypoglycemia, and how to collect appropriate information for each episode of hypoglycemia. Hypoglycemia may be identified by spontaneous reporting of symptoms from participants, whether confirmed or unconfirmed by simultaneous glucose values, or by blood glucose samples collected between study visits.

Monitoring of participant blood glucose levels

Each participant will have a study-provided glucometer that will wirelessly transfer participant SMBG to their study-provided e-diary. Participants should use the glucometer whenever hypoglycemia is experienced or suspected and check glucose values.

A web-interface and reporting system will be available for use by study personnel to view participant e-diary entries, including SMBG, insulin doses, and hypoglycemia information throughout the study. Automated alerts will be transmitted to the investigator any time the participant reports a potential severe episode of hypoglycemia, defined as requiring assistance due to neurological impairment, in the e-diary.

Dose modification and rescue therapy

The dosing algorithm used in the study requires consideration and adjustment of insulin dosing by the investigator based on participant FBG and hypoglycemia events (see Section 6.5).

Participants will be monitored for persistent, severe hyperglycemia and will receive rescue therapy if this should occur (see Section 6.1.2).

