2.3.3. Overall Benefit Risk Conclusion

Considering the clinical data to date and measures taken to minimize risk for the participants in this study, the potential risks identified in association with LY3209590 are justified by the anticipated benefits that may be afforded to insulin naïve participants with T2D.

3. Objectives, Endpoints, and Estimands

Objectives	Endpoints
Primary	
Demonstrate noninferiority of LY3209590 compared to insulin degludec for the treatment of T2D in adults	Change in HbA1c from baseline to Week 52
Key Secondary (Multiplicity Adjusted)	
Demonstrate noninferiority of LY3209590 compared to insulin degludec for participants using GLP-1 receptor agonists	Change in HbA1c from baseline to Week 52
Demonstrate noninferiority of LY3209590 compared to insulin degludec for participants not using GLP-1 receptor agonists	Change in HbA1c from baseline to Week 52
Demonstrate superiority of LY3209590 compared to insulin degludec in selected parameters of glycemic control	
 Change in HbA1c from baseline to Week 52 Time in glucose range between 70 and 180 mg/dL (3.9 and 10.0 mmol/L), inclusive, collected during the CGM session prior to Week 52
Other Secondary	
Compare the effect of LY3209590 to insulin degludec in parameters of glycemic control	
 Change from baseline to Week 26 of HbA1c Time in glucose range between 70 and 180 mg/dL (3.9 and 10.0 mmol/L), inclusive, collected during the CGM session prior to Week 26 Change from baseline to Weeks 26 and 52 of fasting glucose measured by SMBG Glucose variability measured during the CGM session prior to Weeks 26 and 52 Insulin dose at Weeks 26 and 52

Compare the effect of LY3209590 to insulin degludec on safety endpoints	
 Incidence and rate of composite of Level 2 and 3 hypoglycemia events during the treatment period Incidence and rate of composite of Level 2 and 3 nocturnal hypoglycemia events during the treatment period Change from baseline to Weeks 26 and 52 in body weight Measurements collected during CGM sessions prior to Weeks 12, 26, and 52 of 
 Time in hypoglycemia with glucose <70 mg/dL (3.9 mmol/L) Time in hypoglycemia with glucose <54 mg/dL (3.0 mmol/L) Time in hyperglycemia defined as glucose >180 mg/dL (10.0 mmol/L)

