4.6.2.1.10. Hyperglycemia

The study treatments were designed as the treatment of hyperglycemia for diabetes patients. Therefore, the hyperglycemia is usually not reported as an AE in diabetes studies. However, if a participant develops severe, persistent hyperglycemia after randomization, a rescue therapy will be considered. A listing of participants who receive rescue medication will be provided.

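### Two of the three rescue cut-offs in Protocol 6.1.2 are not the same value in mg/dL and mmol/L; the effect is small and the correction is to wording

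*Protocol*

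**What the plan says.** The table in Protocol 6.1.2 has three rows, each a cut-off for the average FBG over a 2-week period:

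- ">270 mg/dL (15 mmol/L", for the period "From Visit 15 until 17 (Week 12 to 16";
- ">240 mg/dL (13 mmol/L", for Weeks 16 to 20;
- ">200 mg/dL (11 mmol/L", from Week 20 to the end of treatment at Week 52.

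All three are strict inequalities. Nothing in 6.1.2 says which unit governs. Meeting a cut-off leads the investigator to consider rescue, after checking compliance and ruling out an acute cause; it does not start rescue by itself. The investigator must confirm and document that the criteria were met before rescue begins.

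Rescue matters to the analysis because it is one of the two intercurrent events in both estimands (Protocol Section 3). Under SAP Section 3, the start of the first rescue medication is a data cut-off in EAS2, the set for the efficacy estimand used outside the United States. EAS1, the set for the United States analysis, keeps all measurements whether or not rescue was used.

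**The concern.** A strict cut-off written in two units should pick out the same participants in either unit. In the second and third rows it does not. A participant with the same 2-week average could qualify for rescue to be considered at one site and not at another, solely because of the unit the site works in. Since rescue ends a participant's data in EAS2, the inconsistency could in principle carry through to which HbA1c values enter the primary analysis outside the United States.

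**Working it through.** **Inputs.** The three unit pairs come from Protocol 6.1.2. The conversion factor follows from the protocol's own pairs: "Time in hyperglycemia defined as glucose >180 mg/dL (10.0 mmol/L" in the Section 3 objectives table gives 180 / 10.0 = 18 mg/dL per mmol/L, and the Level 2 hypoglycemia limit in 8.3.6 gives 54 / 3.0 = 18.

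**Step 1: reproduce the printed figures.** mmol/L = mg/dL / 18.

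- 270 / 18 = 15.00, printed 15
- 240 / 18 = 13.33, printed 13
- 200 / 18 = 11.11, printed 11

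All three printed figures are correct roundings to a whole number. At one decimal they would be 15.0, 13.3 and 11.1.

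**Step 2: convert the printed mmol/L figures back.** mg/dL = mmol/L × 18.

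| Row | Printed mg/dL | Printed mmol/L × 18 | Gap |
|---|---|---|---|
| Weeks 12 to 16 | 270 | 15 × 18 = 270 | 0 |
| Weeks 16 to 20 | 240 | 13 × 18 = 234 | 6 (6 / 240 = 2.5%) |
| Weeks 20 to 52 | 200 | 11 × 18 = 198 | 2 (2 / 200 = 1.0%) |

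A more exact factor of 18.016 gives 234.2 and 198.2 mg/dL, so gaps of 5.8 and 1.8 mg/dL.

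**Step 3: an example.** An average of 237 mg/dL at Week 18 is 237 / 18 = 13.2 mmol/L. It exceeds 13 mmol/L but not 240 mg/dL.

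**Step 4: compare with other conversions.** The abbreviations appendix (Protocol 10.9) pairs 250 mg/dL with 13.9 mmol/L; 13.9 × 18 = 250.2, a gap of 0.2 mg/dL. The titration limits in 6.5 are less exact: 120 is paired with 6.6 (118.8 mg/dL, gap 1.2, 1.0%) and 140 with 7.7 (138.6 mg/dL, gap 1.4, 1.0%). In relative terms the 200/11 gap is no larger than these. The 240/13 gap is the one that stands out.

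**Step 5: how many participants could fall in the bands.** The documents give no distribution of average FBG, so this is an assumption: normal, with mean μ from 130 to 190 and SD σ from 30 to 50 mg/dL. The share in a band from a to b is Φ((b − μ)/σ) − Φ((a − μ)/σ).

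- 234 to 240 mg/dL: from 0.01% (μ = 130, σ = 30) to 3.1% (μ = 190, σ = 50)
- 198 to 200 mg/dL: from 0.2% (μ = 130, σ = 30) to 2.5% (μ = 190, σ = 30)

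These are shares at one moment. More participants could pass through a band at some time during its window. The disagreement arises only between sites that work in different units, and the documents do not give that split.

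**Step 6: reach into EAS2.** SAP 4.3.2 schedules HbA1c for the efficacy estimand at Weeks 2, 4, 12, 16, 26, 36 and 52, so none falls between Weeks 16 and 26. Take the participant at 237 mg/dL in Week 18. If the average stays above 200 mg/dL after Week 20, the third row is met in both units. Whether rescue starts at Week 18 or soon after Week 20, the same scheduled HbA1c values (Weeks 26, 36 and 52) are lost. The 6 mg/dL band therefore changes the HbA1c data mainly for a participant whose average would have fallen to 200 or below by Week 20 without rescue. The 2 mg/dL band after Week 20 is the main remaining route. Self-monitored fasting glucose and insulin dose also enter their models between Weeks 16 and 26 and could lose a few weeks of data, but their endpoints are at Weeks 26 and 52.

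**The case against.** The strongest reply is that nothing is miscalculated. The mmol/L figures are correct whole-number roundings, and the amendment summary describes them as values added to correspond to the mg/dL figures, not as a second set of criteria. Crossing a cut-off only opens an investigator's assessment, so a difference of 1.0% to 2.5% need not change what is done. All of this stands, and it keeps the point minor. It does not remove it: 6.1.2 prints both figures as cut-offs, and a site using the table is not told to treat one as approximate.

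A reader might infer more in two ways, and the documents support neither.

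- **That sites will apply different rescue rules.** The documents show only that they could, in two narrow bands and at the investigator's discretion.
- **That the text promises rescue from randomization while the table begins at Week 12.** The wording invites this: "If a participant develops severe, persistent hyperglycemia after randomization" in 6.1.2, "Participants will be monitored for persistent, severe hyperglycemia and will receive rescue therapy if this should occur" in 2.3.1, and "if a participant develops severe, persistent hyperglycemia after randomization, a rescue therapy will be considered" in SAP 4.6.2.1.10. But the sentence in 6.1.2 goes on to tie rescue to the conditions in the table, the sentence in 2.3.1 ends with a cross-reference to 6.1.2, and SAP 1.2 makes rescue depend on the protocol criteria being met. SAP 4.6.2.1.10 has no such qualifier, but it only introduces a listing of rescued participants. The amendment summary records that the timing was revised after regulatory feedback, and Week 12 is when weekly titration ends (Protocol 4.3). Sites are also not without provisions before then: 6.8.3 covers acute therapy for up to 14 days and changes to background agents for safety, and 7.1 covers stopping study insulin. This is a start date left implicit, not a contradiction.

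**Conclusion.** The point holds in a limited form. Two of the three rescue cut-offs differ between units, by 6 mg/dL in Weeks 16 to 20 and 2 mg/dL in Weeks 20 to 52. Severity is minor.

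No bias in the treatment difference is shown. If a site's unit follows its country, which is an assumption because the documents do not say so, stratifying randomization by country (Protocol 6.3) should balance the effect between arms. No sample size, power or alpha figure depends on it. What remains is a small inconsistency across sites in who is considered for rescue and, mainly through the 2 mg/dL band after Week 20, in where EAS2 HbA1c data stop. The shares of participants given above rest on an assumed glucose distribution and show only the order of size.

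**What to change.** In Protocol 6.1.2, reconcile the two units in each row so that both state the same threshold, with mmol/L at the one-decimal precision used for most other glucose cut-offs, and tell sites which unit governs. Which figures are intended is for the sponsor to settle; none is proposed here.

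Optionally, add a sentence to 6.1.2 confirming that the table's start at Week 12 is intended, and align 2.3.1 and SAP 4.6.2.1.10 with it.

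The cost is a wording change and a short memo to sites. It needs no new data, participants or analyses.
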